11.1.1.1. Mixed Model Repeated Measures Analysis (MMRM)

The absolute values specific parameters specified in Table 2 will be analyzed using a mixed linear model. Treatment and baseline are included as fixed effects. Repeated effect is included for visit. Restricted maximum likelihood method and Kenward and Roger (1997) method for degrees-of-freedom will be used. If a subject's baseline value is missing for a given parameter, then the subject is removed from that parameter's analysis.

This same analysis will be performed with and without multiple imputation as described in Section 7.3.3.5 Each individual/combined active arm will be compared with combined placebo arm.

Unstructured covariance structure will be used, but if convergence is not achieved, then compound symmetry (type=cs) covariance structure will be used.

The following pseudo code will be used.

```
proc mixed data = imputed method=reml;
  by _imputation_;
  class trt01p(ref='Placebo') avisit usubjid;
  model FEV1PP = trt01p avisit trt01p*avisit base / ddfm=kr;
  repeated / subject=usubjid type=un;
  lsmeans trt01p*avisit /pdiff=all cl;
  ods output diffs=lsmdiffl;
run;

proc mianalyze parms(classvar=full)=lsmdiffl;
  class trt01p _trt01p avisit _avisit;
  modeleffects trt01p*avisit;
  ods output ParameterEstimates=lsmdiffEstimate;
run;
```

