11.1.1. Pulmonary Function Tests (PFT)

Key PFT Endpoints

Due to patient-to-patient variability with observed values of PFT measurements (FEV1, FVC, DLco etc), the Percent Predicted (“PP”) versions of these endpoints will be the key PFT endpoints for summary, statistical analyses and interpretation of lung function in ATYR1923-C-002. Additional key PFT endpoints are listed in Table 2 below.

PFT endpoints that are not classified as Key PFT endpoints will be termed “Supportive PFT endpoints”. Where it is warranted, descriptive summaries and/or plots may be produced for some of the Supportive PFT endpoints. All PFT data will appear in the data listings.

Key PFT Timepoints

For tables and figures, all scheduled visits (Baseline, Weeks 4, 8, 12, 16, 20, 24. except DLco measures at Baseline, Weeks 12, 20 and 24) will be presented, though Baseline, Weeks 4, 16 and 24 are the main timepoints of interest for interpretation of the study.

aTyr Pharma, Inc.
 Study ATYR1923-C-002 Statistical Analysis Plan
 IND#: 133692

FINAL Version 1.0
 2021-08-02

Table 2 PFT Endpoint Classification with Planned Summaries and Statistical Analyses

Endpoint classification	Descriptive Statistics				Endpoint Derivations*			Statistical Modeling	
	Absolute value at each Visit	Change from Baseline at each Visit	% Change from Baseline at each Visit	Line Plot by Treatment	Categorized Change from Baseline at each Visit (+/- 5%)	Categorized Change from Baseline at each Visit (+/-10%)	Worsening	MMRM (on Absolute Value with Baseline as covariate)	RCRM (on Absolute Value with Baseline as covariate)
Key PFT Endpoints									
PP FEV ₁ (%)	x	x	x	x	x	x		x	x
PP FVC (%)	x	x	x	x	x	x	x	x	x
PP FEV ₁ /FVC (%)	x	x	x	x	x	x		x	x
PP DLco (%)	x	x	x	x	x	x		x	x
PP DLco adjusted for HgB (%)	x	x	x	x	x	x		x	x
DLco/VA adjusted for HgB	x	x	x	x	x	x		x	x
Supportive PFT Endpoints									
FEV ₁ (L)	x	x	x	x					
FVC (L)	x	x	x	x					
FEV ₁ /FVC	x	x	x	x					
DLco	x	x	x	x					

aTyr Pharma, Inc.
 Study ATYR1923-C-002 Statistical Analysis Plan
 IND#: 133692

FINAL Version 1.0
 2021-08-02

Endpoint classification	Descriptive Statistics				Endpoint Derivations*			Statistical Modeling	

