11.1.1.2. Random Coefficient Regression Model (RCRM)

Table 2 lists key variables that will also be analyzed in RCRM. This model will include treatment, baseline value and treatment-by-time interaction as fixed effects. Both intercept and continuous time in days are included as random effects. Unstructured covariance structures will be used for slope and intercept. If convergence is not achieved, then compound symmetry covariance structure (type=cs) is used and/or the random intercept may be removed. Restricted maximum likelihood and Kenward Rogers (1997) method for degrees-of-freedom will be used.

This same analysis will be performed with and without multiple imputation as described in Section 7.3.3.5. Each individual/combined active arm will be compared with combined placebo arm.

aTyr Pharma, Inc.
 Study ATYR1923-C-002 Statistical Analysis Plan
 IND#: 133692

FINAL Version 1.0
 2021-08-02

Pseudo code below will be used.

For comparing individual arms with placebo:

```
proc mixed data=imputed method=reml;
  class TRT01P(ref='Placebo') usubjid;
  by _imputation_;
  model &pftparm.=TRT01P BASE TRT01P*ady/noint solution ddfm=kr;
  random intercept ady/subject=usubjid type=un; *unstructured covariance
  structure had half of the trials not converge;
  estimate 'A_V_P' TRT01P*ady 1 0 0 -1/ CL;
  estimate 'B_V_P' TRT01P*ady 0 1 0 -1/ CL;
  estimate 'C_V_P' TRT01P*ady 0 0 1 -1/ CL;
  estimate 'T_V_P' TRT01P*ady 1 1 1 -3/ CL divisor=3;
  ods output Estimates=ran_coef_est(rename=(label=effect));
run;

proc mianalyze parms(classvar=full)=ran_coef_est;
  *class A_V_P B_V_P C_V_P A_V_B B_V_C A_V_C;
  modeleffects A_V_P B_V_P C_V_P A_V_B B_V_C A_V_C;
  ods output ParameterEstimates=rcrm_est;
run;
```

For combined active vs. placebo:

```
proc mixed data=imputed method=reml;
  class TRT01P(ref='Placebo') usubjid;
  by _imputation_;
  model &pftparm.=TRT01P BASE TRT01P*ady/noint solution ddfm=kr;
  random intercept ady/subject=usubjid type=un; *unstructured covariance
  structure had half of the trials not converge;
  estimate 'A_V_P' TRT01P*ady 1 0 0 -1/ CL;
  ods output Estimates=ran_coef_est(rename=(label=effect));
run;

proc mianalyze parms(classvar=full)=ran_coef_est;
  class A_V_P;
  modeleffects A_V_P;
  ods output ParameterEstimates=rcrm_est;
run;
```

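### If the unstructured MMRM fails to converge, its only fallback assumes equal variance at every visit, which can misstate the Week 4 and Week 24 standard errors

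*SAP*

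**What the plan says.** SAP 11.1.1.1 states the covariance rule in one sentence: an unstructured matrix is tried first, but "if convergence is not achieved, then compound symmetry (type=cs) covariance structure will be used". On inference it says "Restricted maximum likelihood method and Kenward and Roger (1997) method for degrees-of-freedom will be used"; no robust (sandwich) variance is named.

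The output is by visit. The pseudo code requests "lsmeans trt01p*avisit /pdiff=all cl", and the text adds "Each individual/combined active arm will be compared with combined placebo arm". SAP 11.1.1 states that "Baseline, Weeks 4, 16 and 24 are the main timepoints of interest for interpretation of the study". Spirometry is measured at six post-baseline visits, DLco only at Weeks 12, 20 and 24.

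The model is run with and without multiple imputation, and the imputed fits are run one dataset at a time. The SAP does not say whether a failure in one imputed dataset changes the structure for that dataset only or for all of them. The quality-of-life MMRM in 11.1.3 also uses an unstructured matrix and has no fallback.

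The same key endpoints are also analysed in 11.1.1.2 by a random coefficient model (RCRM) with a random intercept and a random slope on time in days.

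**The concern.** In a by-visit analysis, the standard error at a visit should reflect the spread at that visit. CS replaces the visit-specific variances with one pooled value. When patients drift apart over time, that value is too large early and too small late. Week 4 intervals would then be too wide. Week 24 intervals would be too narrow and their p-values too small. Both are main timepoints for interpretation.

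The step is also steep: for spirometry the fallback drops from 21 covariance parameters to 2, although workable structures lie between. If the fallback is applied separately to each imputed dataset, results from different covariance structures could be pooled into one estimate.

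**Working it through.** **Inputs from the plan.** Three cohorts of 8 active and 4 placebo give 24 active and 12 placebo patients (SAP 5.1). Comparisons are 8 v 12 for each dose and 24 v 12 combined. Visits and model are as in SAP 11.1.1 and 11.1.1.1. The plan states no standard error, visit variance or correlation, so there is no figure of its own to reproduce.

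**Assumptions.** Two-sided 5% level; the variance patterns below; complete data unless stated.

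**Covariance parameters for v visits.** Unstructured v(v+1)/2; heterogeneous Toeplitz v + (v−1); heterogeneous CS v + 1; CS 2. With six visits: 21, 11, 7, 2. With three (DLco): 6, 5, 4, 2.

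**Does the plan itself allow unequal variance?** With a random intercept and slope, variance at time t is σ0² + 2tσ01 + t²σ1² + σe². It is constant only if the slope terms vanish. CS corresponds to the model without a slope, so the fallback is narrower than the RCRM fitted to the same endpoints.

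**Formula (large sample).** SE under CS ÷ true SE at a visit = sqrt(mean residual variance over visits ÷ residual variance at that visit). Actual type I error = 2[1 − Φ(1.96 × ratio)].

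**Worked case: random slope.** Take baseline variance 1 (0.95 between patients, 0.05 noise), a slope SD of 0.3 baseline SDs over 24 weeks, and a baseline coefficient of 0.95. At fraction u of the 24 weeks, residual variance is 0.95 × 0.05² + 0.05 + 0.95² × 0.05 + 0.09u² = 0.0975 + 0.09u².

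- Week 4: 0.1000. Week 16: 0.1375. Week 24: 0.1875. Mean of six visits: 0.1354.
- Ratios: sqrt(0.1354/0.1000) = 1.16; sqrt(0.1354/0.1375) = 0.99; sqrt(0.1354/0.1875) = 0.85.
- Week 24 type I error: 2[1 − Φ(1.96 × 0.85)] = 9.6%.

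**Simulation at the plan's size.** 36 patients, six visits, the SAP's fixed effects, REML under CS, no true effect, 1,500 runs. A t distribution on 31 df approximated Kenward-Roger. Ranges cover the two comparisons.

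| Assumed truth | SE ratio, Weeks 4 / 16 / 24 (formula) | Type I error, Week 4 | Type I error, Week 24 |
|---|---|---|---|
| Exchangeable | 1.00 / 1.00 / 1.00 | 4.7% | 4.3–4.5% |
| Random slope SD 0.2, 5% noise | 1.08 / 1.00 / 0.91 | not simulated | not simulated |
| Random slope SD 0.3, 5% noise | 1.16 / 0.99 / 0.85 | 1.8–2.1% | 7.8–8.5% |
| Autoregressive 0.97, 3% noise | 1.41 / 0.95 / 0.82 | 0.6–0.8% | 8.7–9.8% |
| Autoregressive 0.95 | 1.64 / 0.94 / 0.79 | 0.2–0.3% | 10.5–10.7% |

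Week 16 type I error stayed between 4.5% and 7.6%. Monte Carlo error is about 1 to 1.5 points.

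**Dependence on size and shape (formula).**

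- SD rising evenly from 3 to 6: mean variance 127.8/6 = 21.3; Week 4 ratio sqrt(21.3/9) = 1.54 (0.3%); Week 24 ratio sqrt(21.3/36) = 0.77 (13.2%).
- SD rising evenly from 4 to 6: mean 152.8/6 = 25.47; ratios 1.26 (1.3%) and 0.84 (9.9%).
- SD 3 at Week 4 and 6 from Week 8 on: mean (9 + 5 × 36)/6 = 31.5; Week 24 ratio 0.935 (6.7%); Week 4 ratio 1.87.
- DLco at Weeks 12, 20 and 24, same SDs: first pattern, mean (17.64 + 29.16 + 36)/3 = 27.6, Week 24 ratio 0.88 (8.6%); second, mean (23.04 + 31.36 + 36)/3 = 30.13, ratio 0.91 (7.3%).

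**Is the unstructured fit likely to fail?** On complete data (autoregressive 0.95), it converged to a positive-definite matrix in all 3,000 runs, with type I error 4.4–5.2%. The routine was not SAS.

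**Do intermediate structures help?** Same truth, 400 runs, all structures fitted to the same data. Week 24 type I error was 12.8–15.0% for CS, 5.2–6.8% for heterogeneous CS and 7.7–10.5% for heterogeneous AR(1). Monte Carlo error is about 2 to 3.5 points. The CS figures exceed those in the table; the formula, at ratio 0.79, gives 12.1%, between the two. Heterogeneous Toeplitz was not simulated.

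**The case against.** The strongest reply is that two things must happen together: the unstructured fit must fail, and the visit variances given baseline must really differ. The documents establish neither. Under an exchangeable truth CS is correct, and 36 patients with six visits can support an unstructured matrix on completed data.

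A reader might take the code comment that the unstructured "structure had half of the trials not converge" as proof that the MMRM already fails. It is not. The comment sits in the RCRM code of 11.1.1.2 and concerns the random intercept and slope matrix, not the repeated-measures matrix. It is at most indirect evidence. Random-slope fits can also fail because slope variance is close to zero, which would point away from growing spread; the documents do not say why these failed.

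The size also depends on shape. The corticosteroid taper is due to finish by Day 50, so spread could rise early and then level off, which gives 6.7% at Week 24 in the step example. Finally, SAP 7.4.1 and 7.5 describe the tests as exploratory, without formal hypothesis testing or multiplicity control, and by-visit SDs will be tabulated.

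All of this stands and limits the point. It does not justify the fallback. A rule written for the case in which the unstructured fit fails should be sound in that case, and the analysis without imputation will face incomplete data. Kenward-Roger works within the assumed structure and does not repair a wrong one.

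**Conclusion.** The concern holds conditionally. If CS is used and variance given baseline grows, standard errors are too large at Week 4 (spirometry only) and too small at Week 24. Simulated Week 24 type I error was about 8% to 11% in the 1,500-run growing-variance cases and about 5% with equal variances. Three of the six key endpoints are DLco-based and have no Week 4; Week 16 is little affected.

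A reader might infer that the plan will produce wrong standard errors, or that the Week 24 error rate is 13%. The documents support neither. The first needs both conditions above. The second assumes an even doubling of the SD, for which they give no basis. The growing-variance patterns are likewise assumptions. Since the analysis is exploratory, this is a cheap improvement.

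**What to change.** In SAP 11.1.1.1, replace the single fallback with a fixed order: unstructured, heterogeneous Toeplitz, heterogeneous CS, and plain CS only as a last resort. For each endpoint, use the first structure that converges in every imputed dataset, apply it to all of them, and report which was used. Run the analysis without imputation through the same order. Apply the same rule to the quality-of-life MMRM in 11.1.3.

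Heterogeneous AR(1) is left out because it controlled Week 24 error less well than heterogeneous CS in the comparison above. Heterogeneous variances remove most of the error, not all: under autoregressive 0.95 the Week 4 standard error was still 10–15% too large with heterogeneous CS.

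The cost is a few lines of SAP text and slightly more programming. The drawback is that one failed imputation can move every fit of that endpoint to a simpler structure.

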6.3.1. Study Conduct During the COVID-19 Public Health Emergency

Note that due to the coronavirus disease-2019 (COVID-19) public health emergency, it is understood that some flexibility may be required around the timing of scheduled study visits beyond the visit windows specified in the Schedule of Assessments (Table 1). In particular, the 4-week Screening period may be extended to 6 weeks, laboratory or clinical tests may be performed locally, and telephone contacts may be utilized to follow patients with delayed or missed study visits.

Patients missing 2 consecutive study drug doses are to have study drug permanently discontinued, complete the EOS visit, and be withdrawn from the study. (Patients who withdraw from the study due to COVID-19-related issues may be replaced; see Section 6.4.3.

Note that COVID-19 screening is not required per protocol; however, each study center is to follow standard institutional practice regarding COVID-19.

All deviations due to COVID-19 are to be documented.

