7.3.3. Missing Data

In general, missing data will not be imputed, unless methods for handling missing data are specified. All study related data that is collected will be included in data listings that will accompany the clinical study report.

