7.3.3.5. Multiple Imputation for PFT Parameters

For PFT, sensitivity analyses will be performed to evaluate the impact of missing data. Where an analysis is specified as “Including Imputation”, it will be performed using the Multiple Imputation (MI) Fully Conditional Specification (FCS), using the proc mi procedure from SAS. The endpoints listed as “Key PFT endpoints” in Table 2 will be imputed by regressing on non-missing values of these variables at other timepoints. The number of imputations will be the percentage number of missingness. The following pseudo code will be used.

```
proc mi data=&pftparm._wide (where=( _NAME_ eq "FEV1PP")) seed=1234
  out=imputed_&pftparm._wide nimpute=pctmissing;
  fcs reg;
  var BASELINE WEEK_4 WEEK_8 WEEK_12 WEEK_16 WEEK_20 WEEK_24;
run;
```

Imputed values for Percent Predicted endpoints are restricted to 0 to 150 to ensure imputed values are consistent with values for patients with sarcoidosis and ensuring that impossible values are not produced (e.g. imputation of negative values).

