11. EXPLORATORY ANALYSES

11.1. Clinical and Biomarker Measures

The following measures (continuous) will be summarized in actual values, change and percent change from baseline for each measured visit. If a parameter is missing at baseline, then the patient will not be included in the analysis of change and percent change from baseline for this parameter. If a post-baseline parameter is missing, then the patient will not be included for that visit in both actual values, change and percent change from baseline. The mITT Set will be used for the analyses below. In addition, all PFT and Quality of Life Questionnaire summaries will also be presented in the EE Set.

Additional exploratory analyses of biomarker data may be performed that is beyond the scope of this SAP and the results from such analyses will be described in a separate report and/or publications.

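### The MMRM pseudo code leaves visit out of the REPEATED statement; in the non-imputed analyses, a skipped visit with no row would make standard errors unreliable, often too small

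*SAP*

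**What the plan says.** SAP 11.1.1.1 specifies a REML mixed model for the six key lung-function endpoints in SAP Table 2. Its text states "Repeated effect is included for visit". The pseudo code below that text has "repeated / subject=usubjid type=un", which names the subject and the structure but not the visit. The visit variable does appear in the CLASS, MODEL and LSMEANS statements. Section 11.1.3 prints the same REPEATED line for the quality-of-life scores and says nothing in prose about a repeated effect.

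Four other provisions decide where this matters:

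- **Imputation, lung function.** "This same analysis will be performed with and without multiple imputation as described in Section 7.3.3.5". The imputation covers the whole profile ("var BASELINE WEEK_4 WEEK_8 WEEK_12 WEEK_16 WEEK_20 WEEK_24"), so imputed data have no gaps.
- **Imputation, quality of life.** None is specified, so the general rule applies: "In general, missing data will not be imputed, unless methods for handling missing data are specified".
- **Missed visits.** SAP 11.1 says "If a post-baseline parameter is missing, then the patient will not be included for that visit". It does not say whether a blank row stays in the data set.
- **Fallback.** "Unstructured covariance structure will be used, but if convergence is not achieved, then compound symmetry (type=cs) covariance structure will be used". This appears in 11.1.1.1 only.

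**The concern.** With an unstructured matrix, each row must be told which visit it belongs to. If REPEATED names no effect, the first row of a patient takes position 1, the second takes position 2, and so on. A patient seen at Weeks 4, 12, 16, 20 and 24, with no row for Week 8, then fills positions 1 to 5 instead of 1, 3, 4, 5 and 6. The Week 24 value is given the variance and correlations of position 5, which other patients fill with Week 20 values.

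Such gaps are foreseen. Protocol 6.3.1 says "telephone contacts may be utilized to follow patients with delayed or missed study visits". Protocol 6.5 counts a patient with 5 of 6 doses as a completer. SAP 10.1.4 provides for dosing that restarts after a missed dose. The worsening rule under SAP Table 2 covers missed visits between two values.

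At stake are the non-imputed MMRMs for six lung-function endpoints and the quality-of-life MMRMs. SAT (8), KSQ (6), LCQ (4) and FAS (3) alone give 21 scores. With 6 visits and 4 comparisons with placebo (three arms and the combined arm), that is 21 × 6 × 4 = 504 p-values per analysis set, unadjusted for multiplicity.

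**Working it through.** The plan states no power, variance or standard-error figure for these models, so there is nothing of its own to reproduce. The check is by simulation.

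**Inputs from the documents.** 36 patients, arms 12 (pooled placebo), 8, 8 and 8; six post-baseline visits; REML; unstructured covariance; fixed effects for treatment, visit, their interaction and baseline.

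**Assumptions, not in the documents.** Four covariances: compound symmetry (correlation 0.8, SD 6), and AR(1) 0.85 with SD constant at 6, rising from 4 to 9, or falling from 9 to 4. Visits skipped at random, 5%, 10% or 20% per interim visit, with the skipped row absent. Kenward-Roger was not applied to either fit.

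**Method.** Each data set was fitted twice: rows placed by visit (correct code) and rows placed by order (printed code). The contrast is the mean of the active arms against placebo. There were 300 replicates at N = 36, and a second set at N = 720 to separate misplacement from small-sample error.

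**Step 1: when nothing happens.** With dropout only, the ratio of the printed-code SE to the correct-code SE is 1.000. Imputed runs have no gaps, and blank rows kept in visit order preserve the positions.

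**Step 2: N = 36, Week 24, printed-code SE / correct-code SE.**

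| Covariance | 5% skipped | 10% skipped | Coverage at 10%, correct → printed |
|---|---|---|---|
| Compound symmetry | 0.979 | 0.960 | 95% → 92% |
| AR, constant SD | 0.976 | 0.953 | 94% → 91% |
| AR, rising SD | 0.958 | 0.923 | 95% → 88% |
| AR, falling SD | 0.992 | not reported | not reported |

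The extremes are 1 − 0.992 = 0.8% and 1 − 0.923 = 7.7%, hence about 1-8%. With falling SD the printed-code SE was the lower one in only half of the data sets. The Monte Carlo standard error of a 95% coverage is √(0.95 × 0.05 / 300) = 1.3 points, but both fits use the same data sets.

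**Step 3: N = 720, Week 24, printed-code model SE / true SE of that estimator.**

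| Covariance | 5% | 10% | 20% |
|---|---|---|---|
| Compound symmetry | 1.00 | 1.00 | 1.00 |
| AR, constant SD | 0.99 | 0.98 | 0.97 |
| AR, rising SD | 0.94 | 0.89 | 0.83 |
| AR, falling SD | 0.99 | 0.99 | 0.99 |

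With the correct code the ratio is within about 2% of 1 throughout. Under compound symmetry the shortfall of Step 2 vanishes, so part of the N = 36 effect is small-sample error in the covariance estimate.

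**Step 4: two sources of error.** For rising SD at 10% skipped, the reported SE is 0.958 of the correct-code SE, while the wrong weights raise the true SE by a factor of 1.071. The correct-code model SE is 0.996 of its own true SE. So 0.958 × 0.996 / 1.071 = 0.891. A ratio r gives large-sample coverage of 2Φ(1.96r) − 1; here 2Φ(1.746) − 1 = 0.919. Misplacement alone thus takes 95% to about 92%.

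**Step 5: direction.** With falling SD, the Week 24 reported SE is larger than with the correct code, by factors of 1.010, 1.027 and 1.053 at 5%, 10% and 20%. At earlier visits the picture differs: at 10% skipped, model SE / true SE is 0.938 at Week 4 and 0.949 at Week 16 with falling SD, against 1.001 and 0.922 with rising SD. Direction and size depend on covariance and visit.

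**The case against.** The strongest reply is that this is a slip in pseudo code and not a chosen method. The text of 11.1.1.1 states the intent, the printed lung-function code runs on imputed data where the shift cannot occur, and an analysis data set may well keep a row for every scheduled visit. Visits at Weeks 4 to 20 are dosing visits that the protocol asks sites to reschedule, and two consecutive missed doses lead to withdrawal, so longer gaps tend to become harmless dropout. The compound-symmetry fallback removes the position effect, and Kenward-Roger may offset part of the small-sample shortfall. The endpoints are exploratory.

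Most of this stands and limits the point. It does not remove it. Section 11.1.3 has no text to override its code and no fallback. The SAP says the code will be used, and no section says that blank rows are kept.

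Two stronger readings are tempting. A reader might infer that Week 12 results are analysed as Week 8 results. They are not: the treatment-by-visit term in MODEL and LSMEANS uses the true visit, and only the covariance position moves. A reader might also infer that standard errors are always understated, with false-positive rates well above nominal. One unfavourable setting does show this. With SD doubling from 3 to 6, lag-1 correlation 0.8 and 15% skipped, 240 simulated trials gave 11.7% false positives at Week 24 against 2.9% with rows aligned, and a mean SE 19% below the true SD. The documents supply neither that covariance nor that skip rate, and Steps 3 and 5 show the effect vanishing or reversing at Week 24 under others.

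**Conclusion.** The omission is certain in both code blocks, and in 11.1.1.1 it contradicts the text. The harm is conditional on a missed visit followed by an observed one, no row for the missed visit, a non-imputed analysis, and a fit that stays with the unstructured matrix. Under those conditions weights and standard errors are unreliable and often too small. The sizes in Step 2 describe plausible settings and are not an estimate for this trial, because they rest on assumed covariances and random skipping and omit the planned Kenward-Roger adjustment. Lung function and quality of life are exploratory endpoints, and the primary (adverse events) and secondary (steroid dose, immunogenicity) analyses do not use this model. It is worth correcting as a code error, but it does not threaten the trial's main conclusions.

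**What to change.** In both 11.1.1.1 and 11.1.3, write `repeated avisit / subject=usubjid type=un;`. In 11.1.3, also add a sentence stating that visit is the repeated effect, so that text and code agree in both places. The change costs one word per block. It leaves the imputed runs unchanged, as it does any data set with no gaps or with blank rows in visit order. It also removes all dependence on row layout and sort order. If the models have already been run as printed, rerun the non-imputed lung-function and quality-of-life models and report any difference.
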